6.3 Populations for Analyses

Efficacy endpoints will be summarized according to the Intent-to-Treat (ITT) population and safety endpoints will be summarized according to the as-treated analysis population. These populations are described briefly below along with other populations.

- **Intent-to-Treat Analysis Population:**

The Intent-to-Treat (ITT) analysis Population is defined to include all subjects randomized into the study for whom Case Report Form (CRF) data indicate that at least one dose of study medication (abatacept or placebo) is administered during the double-blind period.

All subjects who are randomized but never received study medication are to be excluded. Given the blinded nature of this study, it is reasonable to assume that subjects who discontinue prior to the receipt of study medication do so for reasons unrelated to study medication. Subjects are grouped according to the treatments to which they are randomized by IXRS.

ITT analysis population is also referred to as “All Randomized and Treated Subjects”.

- **As-Treated Analysis Population:**

The As-Treated analysis population contains all subjects for whom CRF data indicate that at least one dose of study medication was administered during double-blind period.

Subjects are grouped according to the treatments to which they are randomized, except in cases where information is available, which indicates that a subject receives a different treatment for the entire course of double-blind period. In this case, the subject will be presented by the treatment they actually received.

The As-Treated analysis population will also be referred as “All Treated Subjects”.

- **Per-Protocol Analysis Population:**

The Per-Protocol analysis population is defined as a subset of the ITT analysis population which excludes subjects who have relevant protocol deviations during the double-blind study period. Relevant protocol deviations are those protocol deviations that might affect the primary efficacy endpoint of the study. A programmable list of relevant protocol deviation criteria is included in [APPENDIX 1](#).

The analysis of the primary efficacy endpoint will be repeated in the Per-Protocol analysis population. The Per-Protocol analysis population will exclude subjects with at least 1 relevant protocol deviation.

- **Open-Label Treated Analysis Population:**

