7.2 Study Conduct

Relevant protocol deviations, which could have a major impact on the interpretation of the study results, will be identified prior to the unblinding of the database for all subjects who are randomized and receive double-blind medication.

Relevant protocol deviation criteria, including an assessment of the impact of any Covid-19 related deviations observed are listed in [APPENDIX 1](#).

All subjects with relevant protocol deviations will be identified prior to the final database lock and unblinding of treatment assignment. All relevant protocol deviations will be listed and summarized by treatment group.

Following a case by case review of all incidences of Covid-19 related events (scheduling of visits, accurate receipt of medication) the impact of Covid-19 on the primary endpoint is considered minimal. The Per-Protocol analysis will exclude subjects with Covid-19 related deviations that could potentially impact the primary endpoint.

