Higher values for each component of the IMACS core measures (excluding MMT-8) indicate greater severity of disease. Improvement from baseline in a core measure of the IMACS will be computed as the difference between the baseline (Day 1 pre-treatment) value and the value at a given post-baseline visit. A positive value for improvement from baseline for an individual core measure indicates lesser severity of disease. The IMACS DOI will be defined based on the percent improvement from baseline in each of the IMACS core measure listed in [Section 8.1.1](#).

Percent improvement will be computed as the ratio of improvement from baseline to the baseline value times 100 for an endpoint:

$$\begin{aligned} \% \text{ Improvement} &= 100 * (\text{Improvement from Baseline}) / \text{Baseline Value} \\ &= 100 * (\text{Baseline Value} - \text{Post-baseline Value}) / \text{Baseline Value} \end{aligned}$$

For MMT-8, a higher value implies a lesser severity of disease; the % reduction in muscle strength will also be calculated as:

$$100 * (\text{Baseline Value} - \text{Post-baseline Value}) / \text{Baseline Value}$$

8.1.9 **Determination of IMACS DOI Responders**

Any subject who does not meet the IMACS DOI criteria is considered a non-responder. For IMACS DOI status that cannot be evaluated due to missing data (i.e. MMT-8 not available or less than 5 of the core measures available) the following conventions will be implemented:

- For the primary analysis at Week 24, any subject who prematurely discontinues the trial after receiving study medication will have missing data imputed as a IMACS/DOI non-responder at all scheduled protocol visits subsequent to the point of discontinuation. For the sensitivity analysis of the primary endpoint the data collection post discontinuation from the study will be used in the determination of the DOI status and included in the analyses. The tipping point sensitivity analysis will impute the missing data as described in [Section 7.5.3.2](#)
- Any subject for whom data are missing at a given visit not due to premature discontinuation will have a value for IMACS/DOI response imputed at that given visit. If the given visit is not the last scheduled efficacy visit (Day 169), imputation will depend on the observed responses from the previous scheduled visit and the next scheduled visit. If there are IMACS DOI responses observed at both visits, an IMACS DOI response will be imputed for the given

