missing visit. Else, if a non-response is observed at one of the visits or a response is missing at one of the visits then a non-response will be imputed. If the given visit is the last scheduled efficacy visit (Day 169), the missing response will be imputed as non-response.

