APPENDIX 1 RELEVANT PROTOCOL DEVIATIONS

Pre-randomization

- Myositis Activity:
 - Screening MMT-8 score of 140 or more.
 - Failure to document criteria for currently active IIM or obtain approval from adjudication committee.
 - Diagnosis of Inclusion Body Myositis.
- Medication/Procedure/Other:
 - Use of rituximab within 3 months.
 - Use of immune globulin within 6 weeks.
 - Discontinuation of prohibited medication within 2 weeks.

Post-randomization

- Medication/Procedure:
 - Use at randomization of more than 1 of the allowable immunosuppressant's drugs in the Double-Blind period.
 - Use of corticosteroids above prednisone $\geq 35\text{mg/day}$ (or prednisone equivalent) for > 3 weeks or within 2 weeks of Day 169.
 - Increase of 5 mg or more per day or initiation of more than 10 mg per day of prednisone (or prednisone equivalent) that is unrelated to management of an AE or permitted rescue therapy.
 - All prohibited medication not discontinued at least 2 weeks prior to randomization with the exception of immune globulin (3 months), rituximab (6 months) and d-penicillamine (3 months). Prohibited medication in this context refers to immunomodulatory medications for the treatment of IIM which are not included as immunosuppressant medications. The following list includes examples of specific prohibited medications:
 - ◆ Adrenal Corticotrophic Hormone (ACTH), including analogues.
 - ◆ Sirolimus.
 - ◆ Everolimus.
 - ◆ Mizoribine.
 - ◆ Tofacitinib or other JAK inhibitor.
 - All investigational or approved biologic DMARD therapies other than abatacept (including but not limited to tocilizumab, adalimumab, golimumab, certolizumab, etanercept, infliximab, anakinra, rituximab, etc.).
 - Use of any investigational drug other than study medication.
- Study conduct:
 - Subject missed more than 6 consecutive doses of study medication (abatacept or placebo) during the Double-Blind period or missed more than 4 consecutive scheduled doses of study medication (abatacept or placebo) between Day 141 and Day 169.

Covid-19 Related Deviations

- Unable to attend both Day 141 and Day 169 assessments due to travel/other restrictions.
- For missed doses due to Covid-19 the same rule to define those as a relevant protocol deviation applies as under study conduct above.

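### SAP Appendix 1 keeps a subject who misses only Day 169 because of Covid-19 in the per-protocol set as a non-responder, contrary to the exclusion stated in SAP Section 7.2

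*SAP*

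**What the plan says.** The primary endpoint is IMACS DOI response at Day 169 without rescue (SAP 4.1). For the per-protocol set, SAP 6.3 states: "The analysis of the primary efficacy endpoint will be repeated in the Per-Protocol analysis population". It also states who is removed: "The Per-Protocol analysis population will exclude subjects with at least 1 relevant protocol deviation". The criteria are fixed in advance: "A programmable list of relevant protocol deviation criteria is included in" Appendix 1.

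Appendix 1 has two Covid-19 criteria. One concerns visits: "Unable to attend both Day 141 and Day 169 assessments due to travel/other restrictions". The other concerns dosing: "For missed doses due to Covid-19 the same rule to define those as a relevant protocol deviation applies as under study conduct above".

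SAP 7.2 gives the purpose in general terms: "The Per-Protocol analysis will exclude subjects with Covid-19 related deviations that could potentially impact the primary endpoint". The same section reports a case-by-case review of Covid-19 events, calls their impact on the primary endpoint minimal, and refers to Appendix 1 for the criteria.

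On missing responses, SAP 8.1.9 begins: "Any subject for whom data are missing at a given visit not due to premature discontinuation will have a value for IMACS/DOI response imputed". Neighbouring visits are used only when the missing visit is not the last one. For Day 169, "the missing response will be imputed as non-response".

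**The concern.** The endpoint is read at one visit. If that visit is lost to a travel restriction, the result is fixed as failure, and attendance four weeks earlier does nothing to change it. Yet attendance at Day 141 is exactly what decides whether the subject leaves the per-protocol set.

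Take two subjects with no Day 169 data for the same Covid-19 reason. The one who also missed Day 141 is excluded. The one who attended Day 141 is kept and counted as a treatment failure. Their Day 169 information is identical, and the visit that separates them has no role in the endpoint rule.

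At stake is whether the per-protocol analysis does what Section 7.2 says, and whether two programmers working from the two sections would build the same population.

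**Working it through.** **The plan's own figure (background only).** SAP Section 5 gives about 90% power with 75 per arm, 60% against 33%, two-sided 5%, continuity-corrected chi-squared test. With d = 0.27, the effective size after the correction is n' = n − 2/d + 1/(n d²) = 75 − 7.41 + 0.18 = 67.8. Then z = [d√n' − 1.96√(2p̄q̄)] / √(p₁q₁ + p₂q₂), with p̄ = 0.465, gives (2.223 − 1.383)/0.679 = 1.24, a power of 89.2%. Exact enumeration gives 90.3%. The stated figure reproduces. The point does not depend on it; only the two rates are reused below.

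**Tracing the rules for one subject.** The subject attends Day 141, does not discontinue, and has no evaluable Day 169 assessment because of Covid-19 restrictions.

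1. *Is there a Day 169 value?* Table 8.5-1 assigns Days 128–155 to Day 141 and Days 156–211 to Day 169. For subjects who continue, the latter window closes at the first open-label dose. The windows do not overlap, so the Day 141 assessment cannot serve as Day 169.
2. *How is the gap filled?* By non-response (8.1.9), without reference to Day 141.
3. *Is the visit criterion met?* No. Only one of the two named visits was missed.
4. *Is the dose criterion met?* Not by the missed visit. The last double-blind dose falls in Week 23 (Protocol 4.5.1), so a subject can take every double-blind dose and still miss Day 169.
5. *Result.* With no other Appendix 1 deviation, the subject stays in the per-protocol set as a non-responder. Section 7.2, read alone, would remove the same subject.

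**Size, by assumption.** The documents give no count. Assume k subjects per arm of 75 are affected, missed at random with respect to response. If kept, an arm's expected rate is p(1 − k/75). If excluded, it stays at p and the arm shrinks to 75 − k. For k = 3 in both arms, 0.60 × 72/75 = 0.576 and 0.33 × 72/75 = 0.317, a difference of 25.9 points. Expected difference in points:

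| k | Kept, k in each arm | Kept, abatacept only | Kept, placebo only | Excluded |
|---|---|---|---|---|
| 1 | 26.6 | 26.2 | 27.4 | 27.0 |
| 3 | 25.9 | 24.6 | 28.3 | 27.0 |
| 5 | 25.2 | 23.0 | 29.2 | 27.0 |
| 7 | 24.5 | 21.4 | 30.1 | 27.0 |

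The columns are 0.27(1 − k/75), then 0.60(1 − k/75) − 0.33, then 0.60 − 0.33(1 − k/75). For k = 3 in each arm, the corrected power formula gives 86.6% with the subjects kept and 87.8% with them excluded.

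**An extreme case.** If all three missed abatacept subjects would have responded, 45/75 = 60.0% becomes 42/75 = 56.0% when they are kept. Excluding them gives 42/72 = 58.3%, not 60%. Exclusion then recovers 2.3 of the 4 points.

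**The case against.** The strongest reply is that Section 7.2 already covers this subject. It states the exclusion in general terms, follows a case-by-case review, and requires relevant deviations to be identified before unblinding. A reader might infer from Appendix 1 that the sponsor means to keep these subjects. The documents do not support that, since the stated intent is the opposite. What stands is narrower: Section 6.3 makes Appendix 1 the programmable list, Section 7.2 refers to it, and the list omits the case.

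Second, a reader might take the per-protocol analysis to be the only analysis that protects against Covid-19 effects. It is a general supportive analysis that also covers eligibility, medication and dosing deviations. The tipping-point analysis (7.5.3.2) varies the response probability among missing Day 169 results from 0.14 to 0.86 and is not limited to discontinued subjects. That is a real safeguard, but it leaves the per-protocol set as it is.

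Third, the group is narrow. A late visit inside the window is used as observed. Open-label drug is dispensed at the Day 169 visit (Protocol Table 5.1-3), so a continuing subject would normally be assessed before the window closes. This stands, and it limits the size of the point.

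Fourth, removing subjects because an outcome is missing is itself debatable. But Section 7.2 has already chosen exclusion for this population, and the list should follow it.

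Finally, the word "both" in the criterion might be read loosely as either visit. That reading would exclude subjects who missed only Day 141 and have a complete Day 169 result. The line needs rewording under either reading.

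**Conclusion.** The point holds as an inconsistency between SAP 7.2 and Appendix 1, and it is minor. The operative list does not carry out the exclusion that the text describes, and it separates subjects by a visit that has no bearing on the imputed endpoint.

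It applies only where no evaluable assessment falls in the Day 169 window, the subject has not discontinued, Day 141 was attended, and no other Appendix 1 criterion is met. The number is not given and may be zero; the SAP's own view that the Covid-19 impact was minimal suggests it is small. With the assumed 3 random misses per arm, the gap is 27.0 − 25.9 = 1.1 points.

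Two stronger readings should be resisted. One is that the rule always pulls the difference towards zero: that needs misses balanced between arms or mainly on abatacept, and misses confined to placebo would widen it. The other is that the trial's main result is affected: the intent-to-treat primary analysis does not use Appendix 1 and is unchanged.

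**What to change.** Before unblinding, replace the visit criterion under Covid-19 Related Deviations in SAP Appendix 1 with: *No evaluable IMACS DOI assessment in the Day 169 window due to Covid-19 restrictions.* Evaluable should carry its Section 8.1.8 meaning (at least 5 core measures, including MMT-8), and the window should be that of Table 8.5-1. Appendix 1 then matches Section 7.2, late visits inside the window still count, and a missed Day 141 alone does not exclude anyone.

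The cost is one line in the appendix and the matching line in the deviation program. The per-protocol set loses a few subjects at most, and no other analysis changes.

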APPENDIX 2 MYOSITIS RESPONSE CRITERIA

The final myositis response criteria for minimal, moderate and major improvement in adult dermatomyositis/ polymyositis (DM/PM) and combined DM/PM and juvenile DM clinical trials and studies.

Table 10-2: Myositis Response Criteria

Core set measure, level of improvement based on absolute percent change	Improvement score
Physician global activity	
Worsening to 5% improvement	0
>5% to 15% improvement	7.5
>15% to 25% improvement	15
>25% to 40% improvement	17.5
>40% improvement	20
Patient global activity	
Worsening to 5% improvement	0
>5% to 15% improvement	2.5
>15% to 25% improvement	5
>25% to 40% improvement	7.5
>40% improvement	10
Manual muscle testing	
Worsening to 2% improvement	0
>2% to 10% improvement	10
>10% to 20% improvement	20
>20% to 30% improvement	27.5
>30% improvement	32.5
Health Assessment Questionnaire	
Worsening to 5% improvement	0
>5% to 15% improvement	5
>15% to 25% improvement	7.5
>25% to 40% improvement	7.5
>40% improvement	10
Enzyme (most abnormal)	
Worsening to 5% improvement	0
>5% to 15% improvement	2.5
>15% to 25% improvement	5
>25% to 40% improvement	7.5
>40% improvement	7.5
Extramuscular activity	
Worsening to 5% improvement	0
>5% to 15% improvement	7.5
>15% to 25% improvement	12.5
>25% to 40% improvement	15
>40% improvement	20

The total improvement score is the sum of all 6 improvement scores associated with the change in each core set measure. A total improvement score of ≥ 20 represents minimal improvement, a score of ≥ 40 represents moderate improvement, and a score of ≥ 60 represents major improvement. If one of the core measures is missing then the total score will be missing.

Improvement Score Calculation

The absolute percent change $((\text{post-baseline value} - \text{baseline value}) / \text{range}) * 100$ is calculated for each core set measure. For muscle enzymes, the most abnormal serum muscle enzyme level at baseline (creatinine kinase, aldolase, alanine transaminase, aspartate aminotransferase, lactate dehydrogenase) is used.

The range for each of the core set measures are as follows:

Muscle Enzymes: The enzyme range was calculated based on a 90% range of enzymes from natural history data as follows:

Creatinine Kinase: Range = 15 times the upper limit of normal (ULN)

Aldolase: Range = 6 times the ULN

Lactate dehydrogenase, aspartate aminotransferase, and alanine transaminase: Range = 3 times the ULN.

The ULN is based on what is reported in the lab dataset for each enzyme.

Ranges for other core set measures:

Physician Global Assessment of Disease Activity (PGA) VAS: Range = 10

Patient Global Assessment of Disease Activity (SGA) VAS: Range = 10

Manual Muscle Testing (MMT-8): Range = 150

HAQ: Range = 3

Extramuscular Global Activity (using MDAAT): Range = 10

An improvement score is assigned for each core set measure based on the absolute percent change in the core set measure according to the definition in Table 2.1 above. These individual core set measure improvement scores are then totaled among the 6 core set measures to give the total improvement score.

A total improvement score between 0 and 100 corresponds to the degree of improvement, with higher scores corresponding to a greater degree of improvement.

APPENDIX 3 ANALYSIS PLAN FOR OPEN-LABEL, OPEN-LABEL EXTENSION AND LONG-TERM EXTENSION PERIODS ANALYSIS

Analyses specified in this section will be performed:

- 1) At the end of the open-label period, i.e. after all subjects have completed the 52-week assessment.
- 2) At the end of the open-label extension period, i.e. after all subjects have completed the 76-week assessment (Japan sites only).
- 3) At the end of the long-term extension period, i.e. after all subjects have completed the 3-year assessment and all protocol specified follow-up visits.

For sections “Background and Rationale; Study Description; Objectives; Endpoints; Sample Size and Power; Study Periods, Treatment Regimens and Populations for Analyses; Conventions” and their subsections, see [Section 1-Section 6](#) and [Section 8](#) of SAP for 24-week analysis of the double-blind study period. Any changes or modification to the analysis for the double-blind period will be explicitly presented.

The open-label analysis will include safety assessment for all safety data in the database at the time of the 52-week database lock.

The open-label extension analysis will include safety assessment for all safety data in the database at the time of the 76-week database lock.

The long-term extension analysis will include safety assessment for all safety data in the database at the time of the study final database lock.

11 STATISTICAL ANALYSES

11.1 General Methods

All subjects who were randomized and treated during the open-label period will be included in the open-label analysis. The analyses will be based on the open-label treated analysis population and presented by the double-blind treatment group except otherwise stated.

All Japanese subjects who were randomized and treated during the open-label extension period will be included in the open-label extension analysis. The analyses will be based on the Japan open-label extension treated analysis population and presented by the double-blind treatment group except otherwise stated.

All subjects who were randomized and treated during the long-term extension period will be included in the long-term extension analysis. The analyses will be based on the long-term extension treated analysis population and presented by the double-blind treatment group except otherwise stated.

[REDACTED]

[REDACTED]

[REDACTED]	[REDACTED]
[REDACTED]	[REDACTED]
[REDACTED]	[REDACTED]
[REDACTED]	[REDACTED]

[REDACTED]

11.3 Study Conduct

The relevant protocol deviations are only assessed for the double-blind period and not for the other periods.

11.4 Study Population

Frequency distributions or summary statistics of data pertaining to subject disposition, demographics, baseline characteristics, and medical history will be tabulated and displayed by randomized treatment group for all subjects in the open-label / open-label extension / long-term extension periods. No statistical test will be carried out for comparison of any baseline measurement among treatment groups.

11.4.1 Subject Disposition

The number of subjects randomized, the number of subjects treated in the open-label / open-label extension / long-term extension periods, and the number of subjects who discontinued the open-label / open-label extension / long-term extension periods, together with reasons for discontinuation taken from the eCRF status page, will be tabulated by randomized treatment group.

11.4.2 Demography and Baseline Characteristics

Demographic and baseline characteristics of all subjects in the open-label / Japan open-label extension / long-term extension treated analysis populations; summaries will be presented by the double-blind treatment groups. Continuous variables such as age, weight, and duration of disease will be summarized by randomized treatment group using means, standard deviations and ranges. The distribution of categorical variables such as gender, race and geographic region will be summarized by treatment group using frequencies and percentages. See [Section 7.3.2](#) for variables included in these summaries. This will be based on the data captured on the CRF page, except for the summary of the stratification variables which is based on the IxRS data.

